8.1 Criteria for randomization

Randomization will occur at T2 and T3 study visits. Participants with minimal or modest improvement in pain after the PainGuide run-in (PGIC \geq 2) will be randomized. Participants who have a robust improvement in their pain (PGIC<2) will not be randomized to treatment. These non-randomized participants will still complete the remaining study visits and mini-assessments. In order to assign equal numbers of participants to each of the 4 study interventions, randomization probabilities will account for the fact that certain participants, e.g. because of a contraindication, may be eligible for only 3 of the 4 treatments.

8.2 Randomization method

We will perform randomization using a randomization software or a randomization list created by a statistician to assign participants to a treatment in an unbiased manner. A biostatistician will develop the randomization plan and will create the un-blinded randomization list to be uploaded to the software. This will enable study personnel to obtain treatment allocations and will provide functionality to manage the treatment allocation process. Furthermore, this enables study team members to maintain identifying information from participants. Study staff are not blinded to group assignment. The data analytic team are will get a coded data set and will be able to see interventions assigned to each coded participant. The data analytic team are not part of the clinical research staff and only provide data analysis. The randomization software will also track study treatment-allocation progress and provide documentation of the treatment assignment.

9 Intervention Procedures

After completing the PainGuide run-in period, participants will be assessed using either the light or light plus deep phenotyping assessment battery and those who minimal or modest improvement in their pain (PGIC \geq 2) will be randomized to one of four 8-week treatments. The treatments will be: a) MBSR, b) PT and exercise, c) acupressure self-management, and d) duloxetine. Following the first 8-week treatment period, individuals will be assessed again using either the light or light plus deep phenotyping battery and those who minimal or modest improvement in their pain (PGIC \geq 2) will be re-randomized to receive one of the treatments they did not receive in the first treatment period.

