Note that data from this study will be combined with other similar databases at OSU in a data repository or data bank to support other related or unrelated research, development, and commercial purposes without additional consent from enrolled subjects. In particular, researchers will compare data collected here with similar databases of control, low back pain, and neck pain subjects to understand similarities and differences between these cohorts.

18 Statistical Design and Analysis

The analyses will be led by [name], blind to group assignment. We will focus on predicting differential analgesic responses to treatments and other secondary endpoints (multi-dimensional symptoms, functional outcomes, pain beliefs and coping) based on the longitudinally measured patient phenotypes. The objectives of the mechanistic analysis include development of a tool for prediction of the treatment response based on a multi-dimensional feature panel measured at baseline (a study of treatment effect moderators), as well as gain some exploratory structural insights into the causal relationships between light and deep phenotyping

measures (mediation analysis), thus implicating some of the factors as being part of a causal pathway to a specific treatment benefit. Another key objective of the analytic approach will be to build a toolbox of analytic methods and algorithms of data processing to be able to support unanticipated needs of the Research Project and other Cores with custom method compilation and new methodology development to support emerging hypotheses testing in the course of the project and its collaboration with other MRCs. In the sections below we outline our main analytic approach, as well as the power considerations for testing key hypotheses. See Section 1.3 for summary of when various data points are collected.

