The study aims to identify which interventions are most efficacious for different patient phenotypes. The primary analysis will explore how treatment response depends on patient phenotype. Secondary analyses will compare dynamic treatment regimens by patient phenotype. The SMART study does not include a control group because the efficacy of the four treatments has already been shown for the population of cLBP patients.

[figure not shown]
Study team members will not be blinded to patient treatment assignment.

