### **5.5 Randomization and Blinding**

Blocked randomization will be used for the randomization schedule. Block size will be randomized between 4 and 8 and the ordering of treatment assignments within a block will be random.

Randomization will be performed without stratification. Study recruitment will continue until 408 patients have been randomized into a treatment group at study phase T2. We expect that it will be necessary to recruit approximately 500 patients into the study in order to achieve the target of 408 SMART participants. Based on our previous studies , we expect that approximately 15-20% of patients recruited at study phase T1 will not enter the SMART at study phase 2 due to either response to the PainGuide self-management intervention or withdrawal from the study.

We will perform randomization using a randomization software or a randomization list created by a statistician to assign participants to a treatment in an unbiased manner. A biostatistician will develop the randomization plan and will create the un-blinded randomization list to be uploaded to the software. This will enable study personnel to obtain treatment allocations and will provide functionality to manage the treatment allocation process. Furthermore, this enables study team members to maintain identifying information from participants. The randomization software will also track study treatment-allocation progress and provide documentation of the treatment assignment.

Randomization at T3 will be done similar to the one at T2.

Due to the nature of the study and its interventions, neither patients nor study staff will be blinded

to patients' treatment assignments.

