We will fit the model for all repeated measures ( $Y_{3i}, Y_{4i}$ ) using generalized estimating equations (GEE) with a working independence covariance matrix through the R package *gee*. We will use robust standard errors for variance estimation to account for the use of repeated measures. Prior to conducting inference, we will assess the functional forms of the predictors and the validity of the assumptions required for joint stage modeling, especially the assumption of constant interaction effects across treatment stages. If the assumptions for joint modeling are violated, we will conduct the primary analysis with stage 1 data only. For inference, we additionally assume  $Y_{3i}, Y_{4i}$  follow a multivariate normal distribution.

The clinical objective of Aim 1 is to show that patient responsiveness to treatment depends on their

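### Protocol section 18 claims a masked analysis, but section 8.2 shows the analysts every participant's arm, and neither document says how masking would work

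*Protocol*

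**What the plan says.** Protocol section 18 opens by saying that a named lead will direct the analyses "blind to group assignment".

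Protocol 8.2 describes what the analysts receive. They get a coded data set and "will be able to see interventions assigned to each coded participant". It adds that "The data analytic team are not part of the clinical research staff and only provide data analysis", and that "Study staff are not blinded to group assignment".

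The SAP makes no claim of a masked analysis. Section 5.1 says "Study team members will not be blinded to patient treatment assignment". Section 5.5 says that "neither patients nor study staff will be blinded". Neither section mentions masking of the analysts.

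SAP 9.1.1 leaves part of the primary analysis open until data are in hand: "Prior to conducting inference, we will assess the functional forms of the predictors and the validity of the assumptions required for joint stage modeling". The assumption it singles out is that treatment-by-phenotype interactions are the same in both stages. If the assumptions fail, the primary analysis falls back to stage 1 data.

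**The concern.** The two Protocol statements describe the same stage of the trial differently, and a reader of section 18 would conclude that modelling decisions were taken without knowledge of arm. Under 8.2 they would not be.

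Treatment is open-label and the primary endpoint, PROMIS Pain Interference, is self-reported. The hypothesised modifiers in SAP 7.3 are each tied to a named treatment. SAP 9.1.1 tests each interaction by rejecting at |W| ≥ 2, and SAP 7.5 applies no multiplicity control. A modelling choice made with arms visible therefore feeds directly into which interactions are declared. The switch from the joint to the stage-1-only model is the most consequential such choice: it changes the data behind the primary result, and no threshold or test is given for deciding it.

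**Working it through.** The plan states no figure on this point, so the check is a comparison of text.

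**1. What is claimed and what is provided**

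| Question | Protocol 18 | Protocol 8.2 | SAP 5.1, 5.5 |
|---|---|---|---|
| Is the lead masked? | Yes | Not mentioned | Not mentioned |
| Is the analytic team masked? | Not mentioned separately | No, arm is visible | Not mentioned |
| Dummy arm codes? | None | None; codes are for participants | None |
| Point of unmasking? | None | None | None |
| Barrier between lead and team? | None | None; the team is only separate from clinical staff | None |

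Separation from clinical staff is independence. It is not masking.

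**2. Which decisions are exposed**

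- *Fixed in advance:* the covariates in 9.1.1 (sex, age, BMI, race, education, T2 score) and the eight light-phenotype interactions.
- *Open until data are seen:* the functional forms, and the joint-versus-stage-1 decision. The second rests on whether interactions are constant across stages, which cannot be examined without some arm variable.
- *Not the analysts' decision:* SAP 8.3 gives the relatedness of protocol deviations to a medical expert.
- *Less exposed:* data reduction and trimming in SAP section 8 follow summaries that first pool all arms, and formal variable selection belongs to Objective 2 (SAP 9.2), which is labelled exploratory.

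**3. Could the open decisions be made under dummy codes?**

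SAP 9.1.1 uses 7 modifiers and 4 arms. The eight hypothesised pairs cannot be picked out without arm names. All 7 × 4 = 28 modifier-by-arm slopes can be, and those 28 contain the eight. Constancy across stages does not depend on what an arm is called, provided that a code means the same treatment at T2 and at T3.

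**4. How well would masking hold?**

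For a hypothesis about one arm, a masked analyst faces 4 candidate arms. The 4! = 24 ways of labelling all four arms is not the relevant count. Even 4 is optimistic if medication data stay in the file: Protocol 4.3.1 lists SSRIs, SNRIs, tramadol and lithium as contraindications to duloxetine, and 8.1 allows such participants to be randomised among three treatments. The arm with no users of these drugs would be duloxetine.

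**The case against.** **The statements may be compatible.** A reader might infer that both cannot be true. Strictly, section 18 describes one lead and 8.2 a team, so a masked lead with an unmasked team is possible. That stands as logic. It does not rescue the text, because no barrier between lead and team is described, and interaction tests tied to named treatments could not be interpreted by someone who stayed fully masked.

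**The claim is narrow.** It is one phrase in the Protocol. Section 8.2 discloses openly that analysts see arms, and the SAP never asserts masking. This stands: the defect lies in the Protocol, not across the whole plan.

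**Other protections exist.** A reader might infer that masked analysis is the only safeguard left in an open-label trial. It is not. Hypotheses are named in advance, the primary analysis is by intention to treat, first summaries pool the arms, cross-validation is planned, and the analysts are separate from clinical staff. These reduce the risk but do not remove the discretion in 9.1.1.

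**No error rate can be attached.** A reader might put a number on the bias by supposing that the best of several model versions is kept. With four versions, the chance of |z| > 1.96 under the null is 13.0% at a correlation of 0.7 between versions, 11.4% at 0.8 and 8.0% at 0.95; with two versions at 0.95 it is 6.5%. Neither the number of versions nor the correlation comes from the documents, and the calculation presumes deliberate picking. It shows what is possible and estimates nothing.

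**Pre-specification is simpler.** Fixing the forms and the switching criterion in the SAP would achieve much of the same. That is fair, and it is the second route under the fix.

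**Conclusion.** Wrong as written. The Protocol claims a blind analysis that its own procedures do not provide. The exposure is confined mainly to two decisions in SAP 9.1.1, the functional forms and the joint-versus-stage-1 switch; the lack of a criterion for the switch makes it the more serious. SAP 9.1.2 inherits both, since it uses the same strategy for the deep-phenotype model.

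The direction and size of any bias cannot be derived from the documents. They do not support a reading that the analysts could steer deviation classification, or that the eight light-phenotype interactions are themselves open to choice. The conclusion assumes that no masking procedure exists outside the Protocol and SAP. If one does, it should be cited in both.

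**What to change.** Reconcile Protocol 8.2 with section 18 by one of two routes.

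**Route 1: carry out the masking.**
- Give analysts the arms under dummy codes that keep the same meaning at T2 and T3.
- Withhold fields that reveal arm: MBSR and PT session questionnaires, pill counts, AcuWand data, and medication and contraindication data. Adverse-event data should be considered for the same list.
- State in the SAP the criterion for using the joint model.
- Record the functional forms and the joint-versus-stage-1 decision in a dated note, then unmask and fit the 9.1.1 and 9.1.2 models.
- State in 8.2 and section 18 who is masked, to what, and until when.

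**Route 2: drop the claim.**
- Delete the blinding phrase from section 18 and describe the analysis as unblinded.
- Fix the functional forms and the switching criterion in the SAP before analysts receive outcome data with assignments.

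Under either route, leave deviation classification with the medical expert.

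Route 1 costs one masked data cut and a small delay, and the masking will be imperfect. Route 2 costs a Protocol edit and a SAP edit. Neither changes patients or visits.

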9.1 Mindfulness-Based Stress Reduction (MBSR)

Participants randomized to MBSR will meet for 8 weekly 2-hour group sessions and one 6-hour “retreat” with a masters-level or higher therapist formally trained in MBSR (with minimum of MBSR “teacher qualification” by UCSD Center for Mindfulness or equivalent) and with experience working with chronic pain patients. MBSR for pain is manualized and includes all the components of standard MBSR^{23,80,81} and exercises for enhancing sensory, interoceptive, and proprioceptive attention and meta-cognitive present-moment awareness with a compassionate, non-judgmental stance. In-session exercises include the raisin exercise, body scan, and sitting mindfulness meditation on the breath, sensations, emotional states, and thoughts. Each session includes practicing formal mindfulness exercises, dialogue and “mindful inquiry” with the therapist and group, and a series of didactic instructions on stress and pain physiology and psychology and using mindfulness for coping with stress and pain in daily life. Patients are asked to practice daily formal mindfulness at home using assigned audio recordings of 30-45-min guided mindfulness exercises (i.e., body scan, mindful movement, stretching/gentle yoga, and sitting meditation) streamed from a patient-specific study link through a platform like Qualtrics. MBSR therapists will be supervised by co-investigator [name]. All visits will take place at the Domino Farms, Burlington building Back & Pain Center or the CPFRC or virtually on a HIPAA compliant virtual

platform like Zoom. Table 3 below describes the frequency of surveys and communications to the participants during the MBSR intervention.

Table 2 Schedule of Activities for the MBSR intervention

Session	Intervention	Outcomes measured
1	Introducing Mindfulness Meditation: Doing to Being	
2	Perception & Knowing Are Different	Chronic Pain Acceptance Questionnaire (CPAQR-8) & Experiences Questionnaire (EQ-4)
3	There is Pleasure & Power in Being Present	
4	Stress Reactivity	Chronic Pain Acceptance Questionnaire (CPAQR-8) & Experiences Questionnaire (EQ-4)
5	Stress, Mindful Awareness & Responding	
6	Stressful Communications	Chronic Pain Acceptance Questionnaire (CPAQR-8) & Experiences Questionnaire (EQ-4)
7	How Do I Best Take Care of Myself?	
8	Endings Are Beginnings	
6-hour mini retreat	Occurs between weeks 5-7	

9.1.1 Participant Adherence- MBSR

Participants will also be asked to keep a log of study related activities completed at home. Attendance will be taken at each MBSR session. A check in call will be made by the study team 48 hours after starting the treatment to address any patient questions or concerns. Patient homework adherence can be estimated by download count of each mp3 on streaming site.

9.1.2 Standardizing Assessment and Intervention- MBSR

Delivery of the intervention will be facilitated by in-session therapist checklists. All sessions will be audiotaped, and 20% will be observed and scored for adherence and fidelity.⁸²

9.2 Physical Therapy and Exercise (PT)

Participants randomized to PT will meet with the physical therapist twice a week for a 1-hour session for weeks 1 and 2 and then weekly for the remaining 6 weeks (Table 3). For more details, see Physical Therapy Manual. After taking a thorough history, an examination is performed. This examination includes self-reported pain severity and disability as well as clinical assessment such as valuation of strength/endurance, neural mobility, range of motion of the spine and hips, mobility of vertebral segments, and movement patterns that are difficult or avoided (i.e., directional preference). The physical therapist will tailor a program to the participant's needs according to recommended PT practice guidelines that will include in-person treatment, home exercise prescription, and encouragement of progressive, low-intensity, submaximal fitness and endurance activities, such as walking.^{53,83} The in-person treatment focuses on three main areas: mobilization (i.e., gaining joint mobility), flexibility (soft tissue and neural mobility), and strengthening (see supporting documents for PT Treatment Manual). Manual therapy is a main treatment component, and exercises include repeated directional preference movements, trunk flexion and stabilization. Exercises address both specific deficiencies noted in evaluation, as well as coordination of body motions. Participants are will be given a home program of exercises to be done daily and asked to engage in daily walking with a set goal based on the individual's capacity and current fitness level. Walking was selected as the aerobic exercise of focus for this treatment because it is recommended for patients with all levels of pain severity, is highly feasible to complete, and has

shown effects on outcomes such as pain and disability.^{84,85} At weekly visits with the physical therapist, participants will discuss progress toward meeting their walking goal and adherence to the home exercise program. Based upon the progress, the PT will make any necessary modifications (such as increasing the walking goal, adding or refining home exercises). All visits will occur at the Burlington building, [name].

Table 3 Schedule of Activities for the Physical Therapy & Exercise Intervention

Sessions (week)	Aerobic Warm Up	Manual Therapy	Mobility	Questionnaires
1&2 (week 1)	5 minutes	None	Directional preference	Oswestry Disability Index (ODI) (session 1 only) Numeric Pain Rating Scale (NPRS)
3&4 (week 2)	5 minutes	No more than 15 minutes	Continue directional preference and add hip stretches as indicated	Numeric Pain Rating Scale (NPRS)
5 (week 3)	5 minutes	No more than 15 minutes	Same as previous visit	Numeric Pain Rating Scale (NPRS)
6 (week 4)	5 minutes	No more than 15 minutes	Same as previous visit	Patient global impression of change (PGIC) and Oswestry Disability Index (ODI) and Numeric Pain Rating Scale (NPRS)
7 (week 5)	5 minutes	No more than 15 minutes	Same as previous visit	Numeric Pain Rating Scale (NPRS)
8 (week 6)	5 minutes	No more than 15 minutes	Same as previous visit	Numeric Pain Rating Scale (NPRS)
9 (week 7)	5 minutes	As indicated	No more than 5 min	Numeric Pain Rating Scale (NPRS)
10 (week 8)	5 minutes	As indicated	No more than 5 min	Numeric Pain Rating Scale (NPRS), Patient global impression of change (PGIC) and Oswestry Disability Index (ODI)

9.2.1 Participant Adherence- PT and Exercise

Participants will be asked to keep a log of the home exercises they are able to complete and the time spent on each activity. Attendance for the scheduled PT sessions will also be recorded. A check in call will be made by the study team 48 hours after starting the treatment to address any patient questions or concerns.

9.2.2 Standardizing Assessment and Intervention- Physical Therapy and Exercise

9.2.2.1 Standardizing Examination

Baseline examination will be performed by a physical therapist investigative team. These assessors will go through a two-hour training session to standardize examination procedures. During training, special tests will be reviewed in order to ensure correct performance of measures. Assessors will also review inclusion and exclusion criteria. A checklist will be provided in the standardized examination template to ensure that participants meet eligibility requirements. Fidelity checks will be completed on a semi-annual basis.

9.2.2.2 Intervention Training

Study faculty and residents currently enrolled in or recently graduated from the Michigan Medicine - University of Michigan Orthopedic Residency Program will provide all intervention. Within the curriculum, residents

receive detailed, standardized instruction on research methods and intervention techniques. Residents who will be providing intervention will undergo an additional two-hour training and follow the BACPAC PT training manual (see supporting documents). The program director, [name], will provide coverage of care as needed and oversee intervention training. All residents will receive PEERRS training and be added to the IRB.

9.3 Acupressure

The self-acupressure intervention will be delivered using the modified MeTime Acupressure mobile app in addition to in-person instruction via study staff. The MeTime Acupressure app was developed in association with patient focus groups (six focus groups each of eight to ten women) and the University of Michigan 3D Media Laboratory (screen shot examples in Figure 7). The MeTime Acupressure app will be loaded onto computer tablets or smart phones by the participants. Participants will also receive an AcuWand to be used in association with the acupressure app to help participants apply the correct amount of pressure to acupoints (See Figure 6). The self-acupressure intervention points will consist of *Du 20*, *Conception Vessel 6* (CV- 6), *Large Intestine 4* (LI-4), *Stomach 36* (ST-36), *Spleen 6* (SP-6), and *Kidney 3* (K-3) (See Figure 8). Points will be administered bilaterally except for *Du 20*, and *CV-6*, which were done centrally.

Figure 6 AcuWand Device

Participants will be introduced to the MeTime App and AcuWand device at their clinic visit. A research team member will provide the patient with instructions and guide the patient through using the app, the AcuWand and performing Self-

Acupressure. Study participants will be told to perform acupressure once per day and to stimulate each point a circular motion for three minutes. There are 9 acupressure points, totaling 27 minutes of stimulation per day.

